2. SYNOPSIS OF THE CLINICAL INVESTIGATION

TITLE	Heartrate variability during mechanical pressure support ventilation – comparing conventional and variable pressure support ventilation: a cross-over trial					
ACRONYM	Heartrate variability during variable pressure support mechanical ventilation					
NAME OF DEVICE	Infinity Delta Monitor, Dräger, Lübeck, Germany Evita Infinity V500, Dräger, Lübeck, Germany					
DESCRIPTION OF THE PROCEDURES	Retrospectively determine heart rate variability from a standard electrocardiogram (Infinity Delta Monitor) recorded during conventional and variable pressure support mechanical ventilation (Evita Infinity V500). We hypothesize that heartrate variability (median of high frequency components over one hour) will increase during variable pressure support mechanical ventilation as compared to the conventional mode of mechanical ventilation.					
OBJECTIVES	
Primary study objective:
 
To compare the High frequency components (HF) of Heart Rate Variability (median over one hour measurement per patient) between conventional and variable pressure support ventilation.
 
Secondary study objectives:
 
Comparison of applied tidal volumes and in heart rate variability parameters (median of standard deviation of R to R intervals (SDNN), median of high frequency to low frequency ratio over one hour measurement per patient) between conventional and variable pressure support ventilation.
 
Exploratory objectives:
 
Comparison of change in physiological parameters (e.g. systolic and diastolic arterial blood pressure, arterial partial pressure of oxygen, arterial partial pressure of carbon dioxide) between conventional and variable pressure support ventilation.
					
TYPE OF THE INVESTIGATION	Interventional MPG § 40.3 cross-over trial					
PERIOD OF ENROLMENT	First patient First visit	1Q	Last patient First visit	3Q	Last patient Last visit	3Q
CENTER(S) / COUNTRY(IES)	1 center (Medical University of Vienna), Austria					
PATIENTS / GROUPS	60 patients					

Heartrate variability during mechanical pressure support ventilation – comparing

conventional and variable pressure support ventilation: **a cross-over trial**

INCLUSION CRITERIA	
patients undergoing therapy at an ICU
 
patients aged between 18 and 80 years
 
patients intubated and ventilated using SPN-CPAP/PS ventilator mode
 
patients with sinus rhythm in electrocardiogram

EXCLUSION CRITERIA	
patients aged < 18 or > 80 years
 
patients with active heart pace maker / defibrillator
 
patients with absent sinus rhythm in electrocardiogram
 
patients with known severe disease of autonomous nervous system
 
women, who are already known to be pregnant before taking part in this study

COMPARATIVE DEVICE	None.
CONCOMITANT MEDICATION/CON-COMITANT DEVICE	Every therapy / medication / monitoring is allowed as indicated per routine.
EFFICACY ENDPOINTS	
Primary study endpoint:
 
High frequency components (HF) of Heart Rate Variability (median over one hour measurement per patient)
 
Secondary study endpoints:
 
Applied tidal volumes and other heart rate variability parameters (standard deviation of R to R intervals (SDNN), high frequency to low frequency ratio),
 
Exploratory endpoints:
 
physiological parameters (systolic and diastolic arterial blood pressure, arterial partial pressure of oxygen, arterial partial pressure of carbon dioxide).

TOLERABILITY / SAFETY ENDPOINTS	The occurrence of adverse events will be documented.
QUALITY OF LIFE	No quality of life parameters will be measured.
STATISTICAL METHODOLOGY	
Primary Endpoint
 
High frequency components (HF) of Heart Rate Variability (median over one hour measurement per patient)

Secondary Endpoints 
Applied tidal volumes and other heart rate variability parameters (median of standard deviation of R to R intervals (SDNN) or high frequency to low frequency ratio over one hour measurement per patient)

Exploratory Endpoints 
Physiological parameters (systolic and diastolic arterial blood pressure, arterial partial pressure of oxygen, arterial partial pressure of carbon dioxide).

Null and alternative hypotheses: 
Null hypothesis of primary endpoint: there is no difference in the mean heartrate variability (measured as median high frequency components HF over one hour measurement per patient) between variable/noisy pressure support mechanical ventilation compared to conventional pressure support mechanical ventilation.


Alternative hypothesis of primary endpoint: there is a difference in the mean heartrate variability (measured as median high frequency components HF over a one hour measurement per patient) between variable/noisy pressure support mechanical ventilation compared to conventional pressure support mechanical ventilation.

Type-I and -II errors – power 
The significance level was set to 0.05. The study was planned to achieve 80% power.

Interim analysis 
No interim analysis.

Statistical methodology: 
The primary endpoint will be analysed using ANOVA for repeated measurements accounting for group of pressure support mechanical ventilation as well as randomization order, the interaction between group and randomization order as well as gender and age.

Sample size calculation: 
The study was planned based on preliminary data. When the sample size is 52, a single group t-test with a 0.05 two-sided significance level will have 80% power to detect the difference between a mean heartrate variability of 49 ms² in the conventional group and a mean

Heartrate variability during mechanical pressure support ventilation – comparing

conventional and variable pressure support ventilation: **a cross-over trial**

	of 59 ms^2 with variable pressure support mechanical ventilation assuming that the standard deviation of the difference is 25 ms^2 . Due to possible Drop-outs the sample size was set to 60 patients.
STUDY EXTENSION	If collection of data cannot be done in the given time.

3. LIST OF ABBREVIATIONS

EOS	End of study
HF	High frequency components of heart rate variability
HRV	Heart rate variability
ICT	Interventional clinical trial
ICU	Intensive care unit
IEC	Independent ethics committee
LF	Low frequency components of heart rate variability
PaCO ₂	Arterial partial pressure of carbon dioxide
PaO ₂	Arterial partial pressure of oxygen
P _{max}	Maximum pressure support
P _{supp}	Mean support pressure
PSV	Pressure support ventilation
SOP	standard operation procedures
SDNN	standard deviation of R to R intervals of heart rate variability
SPN-CPAP/PS	Spontaneous continuous positive airway pressure/ pressure support
VPSMV	Variable pressure support mechanical ventilation

5. INTRODUCTION

5.1 Background information

Spontaneous-continuous positive airway pressure support (SPN-CPAP/PS) is the routine ventilator mode used in critically ill patients submitted to an intensive care unit (ICU). It guarantees a positive end expiratory pressure, which prevents atelectasis and minimizes weaning time, by supporting the patient's respiratory drive.

A few years ago, this very established ventilation technique was modified by simply altering the rhythm and volume of gas application: instead of administering same tidal volumes in equal time intervals a variation of applied volume as well as altering frequency in ventilation is introduced. This ventilation method is termed noisy pressure support ventilation (noisy PSV) or variable pressure support ventilation (variable PSV). The variation of pressure support will be within a range around a mean support-pressure (P_{supp}) and won't exceed a maximum pressure (P_{max}), which are both adjusted before starting noisy PSV.

Any variation of breathing is physiological and may occur during speaking, moving and many other factors. As novel concept, we propose that such variation of ventilation rhythm and volume may have an important impact on heart rate variability (HRV), which is known as to be an indicator of a healthy heart (Wenckebach, 1914). Since Wolff et al. observed that HRV is an important predictor of mortality in coronary care units, investigation of HRV became more important (Wolf et al., 1978). Thayer and Lane recently found that low HRV is associated with an increasing mortality and proposed low HRV to be a marker for critical illness (Thayer et al., 2010, Thayer and Lane, 2007).

The analysis and further investigation of HRV has therefore become an important issue in modern medicine. Mechanical ventilation plays a pivotal role in ICUs and should be further improved. Mechanical ventilation per se is stressful for the cardiovascular system. Cardiovascular homeostasis is of major importance and we hypothesise that noisy PSV will decrease the stress applied to the human heart measured via heart rate variability (Zipes, 2004, Kleiger et al., 1987, Fozard).

5.2 Rationale of clinical investigation

In this interventional clinical study, we will apply, in a randomized fashion, conventional PSV and variable PSV each for a duration of one hour. During ventilation we will record all data of the patients monitor, including the electrocardiogram (ECG), which is routinely monitored in our patients, and respiratory data, to determine HRV parameters retrospectively. All other ventilatory, hemodynamic and pharmacological treatment will be part of the clinical routine. As two modes of ventilation will be compared, this study is an interventional clinical cross-over trial.

Primary study objective:

To compare the high frequency components (HF) of Heart Rate Variability (median over one hour measurement per patient) from ECG data between conventional and variable pressure support ventilation.

The following parameters will be measured and calculated:

- ECG waveform at 200 Hz
- Pulse pressure waveform as part of the clinical routine
- Arterial blood gas analysis at the beginning and end of each ventilation mode
 - Arterial partial pressure of oxygen (PaO_2)

Heartrate variability during mechanical pressure support ventilation – comparing conventional and variable pressure support ventilation: a cross-over trial

- Arterial partial pressure of carbon dioxide (PaCO₂)
- Arterial pressure waveform if part of the clinical routine
- All respirator data

6. OBJECTIVES OF THE CLINICAL INVESTIGATION (HYPOTHESIS)

6.1 Primary Objective (Hypothesis)

Primary endpoint is the High frequency component (HF) of the heart rate variability. For each patient a median of the HF-curve over one hour treatment will be calculated. This value is chosen, since the median of high frequency components is stable to measurement related artefacts.

Null hypothesis of primary endpoint:

There is no difference in the mean heartrate variability (median high frequency components HF over a one hour measurement per patient) between variable/noisy pressure support mechanical ventilation compared to conventional pressure support mechanical ventilation.

6.2 Secondary Objectives (Hypothesis)

Comparison of applied tidal volumes and other heart rate variability parameters (median standard deviation of R to R intervals (SDNN) and median high frequency to low frequency ratio over one hour measurement per patients) between conventional and variable pressure support ventilation. Note that also for the secondary parameters, the median over a one hour continuous measurement per patient will be used for statistical analyses.

6.3 Exploratory Objectives

Comparison of change in Physiological parameters (systolic and diastolic arterial blood pressure, arterial partial pressure of oxygen, arterial partial pressure of carbon dioxide) between conventional and variable pressure support ventilation. In contrast to the primary and secondary parameters, the exploratory parameters are not measured during the whole study duration (one hour per treatment) but at the beginning and end of each treatment.

7. DESIGN OF THE CLINICAL INVESTIGATION

7.1 Population

This study is an interventional cross-over trial in N=60 patients.

7.1.1 Subject population

The study will include subjects between 18-80 years undergoing therapy at an anesthesiological ICU (ICUs: 9D, 13B1, 13C2). No absent sinus rhythm and no active implanted pacemaker or defibrillator is allowed. Participants will be informed and sign the written informed consent form after extubation and improvement of clinical condition.

7.1.2 Inclusion criteria

- patients undergoing therapy at an ICU
- patients aged between 18 and 80 years
- patients intubated and ventilated on SPN-CPAP/PS mode
- patients with sinus rhythm in electrocardiogram

7.1.3 Exclusion criteria

- patients aged under 18 or over 80 years
- patients with active heart pacemaker/defibrillator
- patients with absent sinus rhythm in ECG
- patients with severe autonomous nervous system disease
- women, who are already known to be pregnant before taking part in this study

7.2 POINT OF ENROLMENT

The subjects will be recruited on ICUs from the Department of Anaesthesia, General Intensive Care and Pain Management. The study will be performed in accordance with the Declaration of Helsinki (1964), including current revisions and the study protocol will be submitted to the Ethics Committee of the Medical University of Vienna for approval. The subject's consent will be collected after extubation and clinical improvement, as far as possible regarding the patient's state of health. All subject names will be kept confidential in the investigators files. Subjects will be identified throughout documentation and evaluation by the number allotted to them during the study. The subjects will be informed that all study findings will be stored and handled in strictest confidence. A data protocol in case report form will be used.

7.2.1 Females of childbearing age

Females of childbearing age will be included.

7.2.2 Duration of the clinical investigation

The duration of the clinical cross-over trial is one year. First, subjects will be included in the clinical study according to inclusion and exclusion criteria. The order of the two interventions will be randomized. According to the randomization, subjects will be allocated first to conventional PSV (duration one hour) then to variable PSV (one hour) or vice versa. Thereafter, the study observation period will be over. Subjects will not have to come to follow up visits or investigations.

7.3 Withdrawal and replacement of subjects

7.3.1 Criteria for withdrawal

Discontinuation from the study is to be understood when the subject did not undergo the end of study (EOS) examination and/or all pivotal assessments during the clinical investigation.

Subjects must be withdrawn under the following circumstances:

- at their own request
- if the investigator feels it would not be in the best interest of the subject to continue
- if the subject violates conditions laid out in the consent form / information sheet or disregards instructions by the clinical investigation personal

- in case of severe medical emergency (e.g. cardiac arrest, reanimation)

In all cases, the reason why subjects are withdrawn must be recorded in detail in the case record file (CRF) and in the subject's medical records. Should the clinical investigation be discontinued prematurely, all clinical investigation materials (complete, partially completed and empty CRFs) will be retained.

7.3.2 Follow-up of patients withdrawn from the clinical investigation

In case of premature discontinuation, no follow-up will be performed. Replacement policy

Patients excluded from the study for any of the reasons above will be replaced.

7.4 Premature termination of the clinical investigation

The sponsor has the right to close this clinical investigation at any time. The internal ethical committee (IEC) and the competent regulatory authority must be informed.

8. METHODOLOGY

The study will be performed for the time of HRV measurement (one hour conventional PSV followed by one hour variable PSV, in total two hours without interruption, randomized fashion).

8.1 Treatment duration and modification

Patients will be screened for eligibility before ventilation-mode switch according to inclusion and exclusion criteria.

8.2 Medical Devices

All devices used in the present cross-over trial are part of the clinical routine (Evita Infinity V500 and Infinity Delta). No extra medical device will be used. Both ECG recording and classical as well as variable PSV ventilator modes are used in routine clinical ICU therapy.

8.2.1 Manufacturer (Model or Type Number including software and accessories):

Storage Instructions:

Manufacturer: Dräger, Model: Evita Infinity V500, Serial Number: Clinical routine ventilation on ICU

Manufacturer: Dräger, Model: Infinity Delta, Serial Number: Clinical routine monitoring on ICU

8.2.2 Installation and handling instructions

According to clinical routine instructions.

8.2.3 Intended use

According to clinical routine instructions.

8.2.4 In-/Decrease of the treatment frequency

Not applicable.

8.2.5 Interruption of the treatment

The treatment will be interrupted in case of technological failure, emergency situation, unstable cardiovascular or pulmonary conditions, cardiac arrest and cardiopulmonary reanimation.

8.2.6 Premature permanent discontinuation of the treatment

Premature discontinuation of the cross-over trial is not planned. There are no interim analyses.

Heartrate variability during mechanical pressure support ventilation – comparing conventional and variable pressure support ventilation: a cross-over trial

8.2.7 Premature permanent discontinuation due to an adverse event

Not applicable.

8.2.8 Premature permanent discontinuation due to another reason than adverse event

Not applicable.

8.2.9 Procedures for subjects' compliance

All recordings will be performed by the investigators.

8.2.10 Concomitant medication

All concomitant medications are allowed.

8.2.11 Interactions, reverse reactions and side effect of the medical device:

Not applicable. All devices used are part of the clinical routine ICU therapy. Both the conventional and variable PSV modes are part of the clinical routine ICU therapy. The arterial blood gas analyses are not part of the clinical routine ICU therapy. Potential risks and side effects of taking arterial blood gas analyses include infection and bleeding only in case of inappropriate usage.

8.3 Randomization and stratification:

Subjects will be randomized to the order of conventional and variable PSV treatment (first conventional PSV and then variable PSV or first variable PSV and then conventional PSV). The randomization will be performed by block-randomization using the online randomization program of the Medical University of Vienna (<https://www.meduniwien.ac.at/randomizer/web/login.php>). There will be no stratification of subjects studied. Only the statistician ([name]) and the responsible person performing measurements ([name]) will have access to the online randomization program.

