8.5 Benefit and risk assessment

Both the Infinity Delta Monitor and the Evita Infinity V500 are part of the clinical routine ICU therapy. Also, the ventilator mode conventional PSV and variable PSV are part of the clinical routine ICU therapy. The only procedures performed in the present cross-over trial is that the ventilator mode will be changed from conventional PSV to variable PSV or vice versa. Therefore, there are no actual risks for the patients during the present study or clinical ICU routine therapy. The only additional procedures attributed to this study is that extra arterial blood gas measurements will be performed during the study. These risks are low, as the person performing the study will be trained in taking arterial blood gas analysis and such procedures are taken also routinely during ICU stay.

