9.1.2 Definition of adverse event and adverse device effect

Adverse events (AEs) are any significant hemodynamic or respiratory impairment (e.g. in- or decrease of systolic or diastolic arterial blood pressure or heart rate or parameters of respiration of < or >30% baseline). Further, any technological problems are defined adverse device effects (ADEs). Such impairments are not expected during the present study.

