9.2.2 SAEs /sADE related to study-mandated procedures

Not applicable.

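### The adverse-event definition does not capture bleeding or infection from the study blood gases as such, although the protocol names these as that procedure's risks

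*Protocol*

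**What the plan says.** **The procedure and its risks.** Protocol section 8.2.11 states: "The arterial blood gas analyses are not part of the clinical routine ICU therapy". It continues: "Potential risks and side effects of taking arterial blood gas analyses include infection and bleeding", and confines these to inappropriate use. Section 8.5 adds: "The only additional procedures attributed to this study is that extra arterial blood gas measurements will be performed during the study". It rates the risk as low, because the operator is trained and this kind of sampling is also done routinely in the ICU. Sections 8.6.3 and 8.6.4 fix the number at two samples per ventilation mode, four per patient.

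**What counts as a safety event.** Section 9.1.2 states: "Adverse events (AEs) are any significant hemodynamic or respiratory impairment". Its examples are changes of more than 30% from baseline in blood pressure, heart rate or respiratory parameters. Adverse device effects are technical problems. Section 9.2 takes the same two categories and adds a potential threat to life. Section 9.2.2, on serious events related to study-mandated procedures, reads "Not applicable".

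**What uses these terms.** The synopsis and section 11.6.3 (safety endpoint, frequencies and percentages), sections 9.5 and 9.5.1 (reporting to the ethics committee), 12.3.1 (monitoring) and 13.2 (reporting to the ethics committee and the authority) all refer to these categories.

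**The concern.** The protocol names specific harms for the one procedure it adds to routine care, then defines its safety events so that those harms have no category of their own. A reader of the final report who sees no adverse events could take that as reassurance about the blood sampling, when it would say little about it.

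The point carries some weight because consent is obtained only after extubation (sections 7.1.1, 7.2 and 8.6.2). Patients undergo the non-routine sampling before they can agree to it, so its harms should be visible in the trial's own record.

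**Working it through.** The question is one of definition. The check sets the sections side by side and then sizes what the safety data could show.

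**1. Can the named harms be classified?**

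| Event related to study sampling | AE (9.1.2) | ADE (9.1.2) | SAE (9.2) |
|---|---|---|---|
| Bleed or haematoma without significant haemodynamic or respiratory impairment | no | no | no |
| Local infection without such impairment | no | no | no |
| Bleed or infection causing such impairment within the observed two hours | yes, but as the impairment | no | yes if potentially life-threatening, again as the impairment |
| Infection appearing after the two hours | not observed (10.1: no follow-up) | no | not observed |

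The examples in 9.1.2 illustrate kinds of impairment. They do not open the definition to other harms.

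**2. Does another section widen the terms?** No. Sections 9.5, 9.5.1, 11.6.3, 12.3.1 and 13.2 use the same terms and give no broader definition.

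**3. What does 9.2.2 add?** Its heading covers serious events only. It does not remove non-serious procedural events; 9.1.2 alone does that. The entry is still at odds with 8.6.3 and 8.6.4, which mandate a procedure, and with 8.2.11, which gives it risks.

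**4. Exposure.** The plan's own count reproduces: 2 samples per mode × 2 modes = 4 per patient. At full enrolment, 4 × 60 = 240 samples.

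**5. What complete recording could show.** With zero events in n patients, the exact one-sided 95% upper bound is 1 − 0.05^(1/n).

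- n = 60 (planned enrolment): 1 − 0.05^(1/60) = 4.9% per patient.
- n = 52 (the number in the power calculation): 1 − 0.05^(1/52) = 5.6% per patient.

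The patient is the right unit, because the four samples are taken within two hours from the same person. Under the present definition neither bound can be stated, since an absence of recorded events does not mean an absence of bleeds or infections.

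**The case against.** **The risk is qualified.** Section 8.2.11 limits it to inappropriate use, and 8.5 calls it low. This lowers the stakes. It does not bring the events into the definition, so the gap remains.

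**The definition is not blind to everything.** A reader might infer that the safety endpoint must return zero procedure-related events whatever happens. The text does not support that. A bleed large enough to produce significant haemodynamic or respiratory impairment during observation is an adverse event under 9.1.2, and a serious one under 9.2 if potentially life-threatening. What is lost is its identity as a bleed, together with every event below that threshold.

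**Section 9.2.2 is narrower than it may look.** It could be read as excluding all events from study procedures. It concerns serious events only.

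**Even good recording would be weak evidence.** It is tempting to take all 240 samples and quote 1 − 0.05^(1/240) = 1.24% per sample. That treats clustered samples as independent, and a delayed infection cannot be assigned to one draw. The per-patient figure is larger, and the trial does not set out to test the low-risk statement; safety is purely descriptive. This stands. It limits what the fix can deliver, but does not justify leaving the named harms out.

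**The comparison is not biased.** Sampling is the same in both modes, so the omission does not distort the contrast between them. This is also correct.

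**Conclusion.** The point holds as an internal inconsistency in safety capture. Sections 8.2.11 and 8.5 name infection and bleeding as risks of the one added procedure. Sections 9.1.2 and 9.2 give these harms no category unless they cause haemodynamic or respiratory impairment, and then only under that label. Section 9.2.2 treats the serious ones as irrelevant. The passages must be reconciled.

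The consequence is confined to the safety endpoint and to reporting. The primary and secondary analyses and the sample size are untouched. The correction is worth making because it is cheap, but the trial does not fail without it.

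The conclusion assumes that a minor bleed, haematoma or local infection is not in itself a significant haemodynamic or respiratory impairment. The 4.9% bound assumes 60 evaluable patients, complete recording and zero events.

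**What to change.** 1. Extend section 9.1.2 so that bleeding, haematoma or infection related to the study blood sampling counts as an adverse event, and extend 9.2 to cover it when serious.
2. Replace the entry in 9.2.2 so that it agrees with the sampling mandated in 8.6.3 and 8.6.4.
3. Add one CRF line for these events, completed at the end of the two hours. This needs no new visit and suits bleeding and haematoma.
4. If later events such as infection are also to be noted, the existing consent contact in 8.6.2 could be used. Sections 7.2.2, 8.6.3 and 10.1, which end observation after the two treatment hours and exclude follow-up, would then need aligning. The protocol should state that this contact does not reach every patient: it takes place only after extubation and transfer, and section 7.2 makes consent depend on the patient's condition. Patients who die or are never extubated would be missed.
5. If a bound is reported when no events occur, give it per patient.

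**Cost:** two definition changes, one replaced entry and one CRF line; step 4, if taken, adds amendments to three further sections. The adverse-event count may look slightly less favourable, and capture of delayed infection will stay incomplete.
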